## **2 BACKGROUND:**

Stroke affects more than 795,000 people per year in the United States. Stroke is a leading cause of long-term disability, reducing mobility and communication skills in more than half of survivors over age 65. Movement deficits are a hallmark of stroke, resulting from weakness or paralysis on one side of the body. Common outcomes of stroke are difficulty walking and reduced walking speed, difficulty using the affected upper arm, rigidity of the limbs, impaired balance, and impaired speech, language, and cognition. Improvements in these deficits are seen during acute recovery after stroke. Early clinical treatments, including physical rehabilitation and medication, aim to build on these improvements and return stroke patients to a certain level of function before hospital discharge. The length of stay in a hospital varies with severity of the stroke and the patient's ability to function in the community. However, determining whether a patient has recovered sufficiently for discharge depends on measures that are subjective and imperfect.

Currently, the monitoring, treatment, and evaluation of stroke patients rely on infrequent clinical assessments, performance-based rehabilitation measures, and patient self-reports. Performance-based rehabilitation measures are limited by lack of sensitivity, reliability, and validity in identifying changes or clinical efficacy of treatment or recovery progression. The quality of patient-reported recovery is limited by recall and rater bias. Thus, there exists a strong need for objective, reliable, and continuous monitoring of stroke patients to assist clinicians and therapists make informed decisions about stroke treatment and recovery.

Body-worn sensor technologies can continuously monitor individuals with stroke and allow clinicians and therapists to offer more customized interventions during clinical procedures. Specifically, a wireless sensing system enables quantitative measures of body function and activity, tracking biometric data and communication or mobility-related activities.

This project proposes continuous monitoring, quantification, and interpretation of recovery during clinical treatment of stroke using non-invasive, portable, real-time body-worn sensors. Clinicians and therapists would have customized access to a patient history of sensor-based biometric and activity data, allowing them to more fully measure recovery and assign treatment after stroke.

Recently, body-worn sensors (heart rate, galvanic skin response, IMUs, accelerometers, gyroscopes) have been used to monitor the function and activity of stroke survivors in a non-systematic manner, either inside or outside a clinical setting. In the section below, we summarize the specific aspects of stroke already monitored in a limited population and present suggestions for other characteristics that can be monitored using continuous and advanced body sensors.

## **3 INCLUSION AND EXCLUSION CRITERIA:**

STU#: STU00205532

### 3.1 Inclusion Criteria

#### Patient group

- Individuals diagnosed with stroke admitted to the Shirley Ryan AbilityLab (inpatient), or individuals in the community who had a stroke (chronic)
- Age 18 or older
- Able and willing to give written consent and comply with study procedures

#### Healthy control group

- Individuals without any known significant health problem (healthy controls)
- Age 18 or older
- Able and willing to give written consent and comply with study procedures

### 3.2 Exclusion Criteria

#### Patient group

- Neurological degenerative pathologies as co-morbidities (such as multiple sclerosis, Alzheimer's disease, Parkinson's disease, etc.)
- Pregnant or nursing
- Skin allergies or irritation; open wounds
- Utilizing a powered, implanted cardiac device for monitoring or supporting heart function (i.e. pacemaker, defibrillator, or LVAD)

#### Healthy control group

- No known history of cerebrovascular accidents or neurological degenerative pathologies (such as multiple sclerosis, Alzheimer's disease, Parkinson's disease, etc.)
- Pregnant or nursing
- Skin allergies or irritation; open wounds
- Utilizing a powered, implanted cardiac device for monitoring or supporting heart function (i.e. pacemaker, defibrillator, or LVAD)

## 4 STUDY-WIDE NUMBER OF PARTICIPANTS:

The exploratory phase of the study will enroll up to 100 subjects as healthy controls, assuming 10% attrition. The study will enroll up to 400 subjects with subacute and chronic stroke for the clinical monitoring at the Shirley Ryan AbilityLab (SRAlab), assuming 50% attrition.

## 5 STUDY TIMELINES:

Inpatients with stroke will undergo up to **four types of assessment** (clinical, swallowing/speech, exercise, and sleep/rest) during inpatient stay, from the time of consent until discharge from the hospital or dropout from the study. **Assessments will be completed a minimum of two times**, including: (1) upon consent (surrounding admission to hospital), and

STU#: STU00205532

(2) at discharge. Assessments will be completed at additional times as schedules allow. Additional visits to monitor stroke recovery over time may be completed at 5 different time points following discharge from inpatient rehabilitation.

Individuals from the community who had a stroke and healthy controls will undergo up to **three types of assessment** (clinical, swallowing/speech, and exercise) **during up to 5 laboratory visits** (expected 2-3 hours). Additional visits may be necessary if technical issues arise or sensor technology changes.

The assessments and their frequency for each cohort are as follows:

Assessment	# times (stroke)	# times (healthy)	Time required for each assessment
Clinical	2-10	5	1-2 hours
Swallowing/Speech	2-10	5	≤ 1 hour
Exercise	2-10	5	1 hour
Sleep and Rest	2-10	0	≤ 1 hours per day for rest, overnight for sleep (until wake)

Procedures for each assessment are described in Section 6.2 (individuals with stroke - inpatient) and 6.3 (chronic stroke and healthy controls).

## 6 PROCEDURES INVOLVED:

### 6.1 Overview and Scope

Sensors can collect the following data from healthy controls and patients with stroke:

- Biometric data, including electrocardiography (ECG), electromyography (EMG), and sweat.
- Movement data from the limbs, including signals from triaxial accelerometers (ACC), gyroscopes (GYR), and magnetometer (MAG).
- Acoustomechanic laryngeal data to detect speech and swallowing events.

The sensors to be used will include commercial wearable devices as well as custom sensors designed by our collaborators, the [name] research group at Northwestern University. Both commercial and custom devices measure combinations of ACC, GYR, MAG, EMG, and ECG, ECG, while the custom sensors measure acoustomechanic laryngeal data and sweat.

Most of these sensors have been previously validated against gold standard measures for healthy controls and individuals with stroke (Table 1). Thus, feasibility of inpatient monitoring (**Aim 1**) will focus on validating these sensors during common clinical tests and mobility-related activities for healthy controls and subjects with stroke.

STU#: STU00205532

Quantification of stroke recovery (**Aim 2**) will involve the development of algorithms to analyze sensor data for healthy and stroke cohorts.

**Table 1.** Validation of wearable sensors (Commercial and custom sensors)

Sensor	Gold standard	Validation	Methods
EMG (250-1000 Hz)	Delsys (2000 Hz)	
SRAlab: Pilot study – similar SNR during plantarflexion MVC for 1 healthy subject at gastrocnemius (GA). Qualitatively similar signal profile during 10MWT for 1 healthy subject at tibialis anterior (TA). Temporal displacement of spikes possibly due to sensor's non-uniform sampling interval
 
SRAlab: In progress (data collected) – 9 healthy subjects and 8 with stroke
	MVC, sensor at GA  10MWT, sensor at TA
ACC (25-500 Hz)	Delsys (148.14 Hz)	
SRAlab: Pilot study – at GA, good correlation with Delsys norms during 10MWT for 2 subjects with stroke.
 
SRAlab: In progress (data collected) – 9 healthy subjects and 8 with stroke
	10MWT, sensor at GA.
GYR (25-500 Hz)	ActiLink GT3X (100 Hz)	
SRAlab: In progress (data collected) – 9 healthy subjects
 
No data for stroke (expected unnecessary: healthy subjects should be sufficient to validate angular velocity at same sampling frequency as GT3X)
	N/A
ECG (250-1000 Hz)	Polar H7 heart rate monitor & V800 watch (1000 Hz)	
SRAlab: Pilot study – good agreement of pNN50 and RMSSD for 3 healthy subjects.
 
SRAlab: In progress (data collected) – 9 healthy subjects and 8 with stroke
	6MWT on treadmill (speed normalized for Fr=~0.16)
Acoustomechanic	Videofluoroscopic	SRAlab: In progress (data	N/A

STU#: STU00205532

laryngeal sensors	measurement	collected on 5 healthy controls and 10 persons with aphasia)	
-------------------	-------------	--	--

## 6.2 Procedures for individuals with stroke (inpatient)

### A. Enrollment, consent, test for exclusion criteria

Individuals with stroke admitted as inpatients to the Shirley Ryan AbilityLab or individuals who had a stroke will be asked to potentially enroll in the study. The study coordinator will assess eligibility based on inclusion criteria, obtain informed consent, and answer any questions from the participant.

Participants will complete a demographics and health intake form, by interview. This information will include: age, gender, race, and medical history.

Prior to discharge, information will also be collected about the participant's living and care in the community – for example, whether they will return to independent or assisted living, and whether they will have a full- or part-time caretaker. Because the anticipated support system for patients may affect readiness for discharge (e.g. someone with full time care would not need as much functional independence as someone living alone, and thus might be discharged earlier), we will be prepared to examine amount of recovery at discharge for subsets of the inpatient population related to community living and care. Participants in this group will also be offered to complete follow up clinical assessments at different time points following their stroke once they have discharged home. Up to 5 additional visit will be completed in a laboratory setting (sessions lasting 1-2 hours).

### B. Sensor instrumentation

Participating individuals with stroke will wear different sensors for each assessment, including clinical, swallowing/speech, exercise, and sleep/rest. The sensor locations for each set are presented in the following sections.

For each sensor location, the skin will be prepped and cleaned using alcohol wipes. Some sensors are placed on the skin using adhesive stickers that minimize irritation. Medical dressing (Tegaderm, 3M) may also be used to ensure adhesion and proper contact with the skin. Following use, sensors will be cleaned with soap and water.

Others will be attached with Velcro straps at lower body including pelvis, thigh, shank and foot. Sensors and Velcro straps will be removed, cleaned, and relocated as needed for different activities in a given assessment.

Different commercial sensors might be used based on their commercial availability. At the current stage, the study will include two main technologies for motion capture, namely Xsens system and BionicPro system.

Xsens Technologies B.V. (or Xsens) is a supplier of 3D motion capture products and inertial sensors based upon miniature MEMS inertial sensor technology. The company has created intellectual property in the field of multi-sensor data fusion algorithms, combining inertial sensors with aiding technologies such as GPS, Motion capture and biomechanical modeling. The Xsens MVN inertial motion capture system is an easy to use, cost efficient system for full-body human motion capture. MVN is

STU#: STU00205532

[figure not shown]
based on Xsens' miniature inertial sensors and wireless communication solutions combined with advanced sensor fusion algorithms, using assumptions of biomechanical models. The MVN system is a full body inertial kinematic measurement system, incorporating synchronized video data. Instant graphical output is provided, including joint angles.

BionicPro system is a set of MEMS inertial sensors commercialized by Ottobock to measure and evaluate the motion of the lower limbs. The data collected by the sensors are elaborated by a base station and displayed on the graphical user interface. The sensors are placed on the pelvis, thighs, shanks and feet by means of clips and straps whose length can be adjusted based on the user's anthropometries. BionicPro sensors measure the acceleration, the angular speed, and the magnetic field of the sensor, and compute information such as the pose of the limbs, the joint angles, the temporal parameters of the gaits.

The battery life of each sensor will depend on which signal modalities are activated for that sensor (e.g. ACC only: 8-35 hours, ACC+GYR: 2-4 hours, ACC+EMG: 11 hours). We will maintain an approximate sensor charging schedule for each participant to facilitate assessment. Research staff and clinical staff will be recruited to assist with sensor charging as needed.

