## F. Sleep and Rest assessment

STU#: STU00205532

Sleep and rest assessment will monitor patients during overnight sleep and during wakeful rest in their rooms. Sensors will measure vital signs and movement in the upper and lower limbs. Sensor placement for this assessment is depicted in Figure 4.

**Figure 4:** Possible locations of sensor placement for inpatient sleep and rest assessment

Sensor Type	Location	Modalities	Purpose	Assessment
a	Left parasternal and mid-clavicular line, Left parasternal line, Left mid-axillary line	ECG	Heart rate (and variability), abnormalities (i.e. ectopy rate)	Sleep, Rest
b	Wrists (bilateral)	ACC+GYR, Actigraphy	Movement detection, light exposure to evaluate sleep events and quality	Sleep
			Movement detection, activity recognition	Rest
c	Hands, feet (bilateral) Forehead, thigh, intraclavicular region, stomach	Skin temperature	Skin temperature to evaluate sleep events and quality	Sleep

STU#: STU00205532

Research staff may record continuous sensor data for various rest-related activities, such as sitting or moving in a wheelchair, for use in activity recognition models.

Clinicians will log sleep and movement events as noticed during their usual patient rounds. After assessment, they will also ask the patient for information about bedtime, wake-up time, total sleep time, sleep latency, wake after sleep onset, naps, any unusual events during the day or night, and rating of overall sleep quality, recording as much information as is communicable by the patient. Logs will be consulted during analysis to compare with the timestamped sensor data.

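### Does the 2-4 hour battery life for ACC+GYR undermine the overnight wrist recording?

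*Protocol*

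**What the plan says.** Three places in the protocol bear on this.

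- **Battery life (section 6.2.B, repeated in 6.3.B).** Life depends on which signals are switched on: "e.g. ACC only: 8-35 hours, ACC+GYR: 2-4 hours, ACC+EMG: 11 hours". The next sentences are the provision for this limit: "We will maintain an approximate sensor charging schedule for each participant to facilitate assessment", and "Research staff and clinical staff will be recruited to assist with sensor charging as needed". Earlier in the same section: "Different commercial sensors might be used based on their commercial availability".
- **Wrist sensors (section 6.2.F, Figure 4).** The modality cell reads "ACC+GYR, Actigraphy". It serves two lines. The sleep line has the purpose "Movement detection, light exposure to evaluate sleep events and quality", and the rest line has "Movement detection, activity recognition". The caption presents the placements as possible ones.
- **Recording time (section 5, assessment table).** Sleep is recorded "overnight for sleep (until wake"). Rest takes at most 1 hour per day. No length of night is given in hours.

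No other ACC+GYR battery life appears, and none is given for an actigraphy device.

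**The concern.** Side by side, the sections seem to plan a recording that the equipment cannot make. If the wrist sensor starts at bedtime with accelerometer and gyroscope both running, and nobody recharges or replaces it, the trace ends after 2-4 hours. The loss would not be random, because it would always fall in the later part of the night.

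Section 6.2.F has clinicians log sleep and movement events, ask the patient about wake-up time, total sleep time and waking after sleep onset, and compare the logs with the timestamped signals. A trace that has already stopped cannot be compared with the wake-up time or with any later event. Aim 1 concerns the feasibility of continuous monitoring, and Aim 2 names sleeping among the activities to be recorded. A foreseeable, systematic gap in a sleep channel would therefore touch the stated purpose of the study.

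**Working it through.** No power or error-rate calculation is involved, and the plan has no derived figure to reproduce. The check compares battery life with recording time.

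**Inputs from the protocol.** ACC+GYR life 2-4 h and ACC-only life 8-35 h (section 6.2.B); rest at most 1 h per day, sleep until waking, at least two assessments (section 5).

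**Assumption.** Length of night: 8 h, with a range of 6-10 h, because the protocol gives none.

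**Formulas.** Coverage of one charge = battery life / night. Charges per wrist = night / battery life, rounded up. Changes per wrist = charges - 1.

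| Assumed night | Coverage at 2 h | Coverage at 4 h | Charges per wrist | Changes, both wrists |
|---|---|---|---|---|
| 6 h | 2/6 = 33% | 4/6 = 67% | 2-3 | 2-4 |
| 8 h | 2/8 = 25% | 4/8 = 50% | 2-4 | 2-6 |
| 10 h | 2/10 = 20% | 4/10 = 40% | 3-5 | 4-8 |

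On an 8 h night the loss is 8 - 4 = 4 h to 8 - 2 = 6 h, or 8-12 h of 16 h over two nights. Even the most favourable pairing (4 h battery, 6 h night) leaves a third unrecorded without a change of sensor.

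**For comparison.** ACC only at its lower limit of 8 h covers all of a 6 h or 8 h night and 8/10 = 80% of a 10 h night. A rest block of at most 1 h fits within 2-4 h.

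**Does the plan commit to ACC+GYR overnight?** The arithmetic bites only if it does, so the wording of Figure 4 decides the matter.

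1. The sleep purpose includes light exposure. Accelerometers and gyroscopes are motion sensors (section 6.1) and do not supply it, so the actigraphy entry is needed on the sleep line.
2. The rest purpose has the same wording as the purpose given for the ACC+GYR+MAG sensors in the clinical and exercise tables (sections 6.2.C and 6.2.E). ACC+GYR fits naturally there.
3. On that reading, ACC+GYR runs for at most 1 h at a time, and the 2-4 h figure is ample.
4. On the other reading, both modalities run all night. The 2-4 h figure would then apply only if the example describes the wrist device used. The protocol does not say so.

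**The case for a change.** The strongest case for acting is that the literal reading is reasonable. Where the other sensor tables offer alternatives within a modality cell, they join them with *or*; Figure 4 uses a comma, which suggests both. Both wrist purposes begin with movement detection, and section 7 derives limb movement from gyroscope as well as accelerometer values, so overnight gyroscope recording may well be intended. The wrist row is also the only one in the Figure 4 table with a motion signal. The charging provision is loose and describes no overnight arrangement, and section 14 mentions round-the-clock nursing in the context of emergencies. One added sentence would remove the doubt.

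Much of this stands. The cell is ambiguous, the protocol does not say which modality runs overnight, and overnight gyroscope use cannot be ruled out. What does not follow is that the plan contains an error. The harm needs the less favourable reading, the example figure applied to an unnamed device, a start at bedtime, no recharge or replacement, and no change of active modality. The protocol leaves every one of these open. Section 6.2.B shows that the authors know battery life depends on the active signals, and it assigns staff to charging.

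The possible remedies bring no demonstrated gain either. Restricting the night to ACC only would be a design preference: it gives up a signal that may be wanted and could still fall short of a 10 h night. Requiring sensor changes would mean 2-6 handlings over an 8 h night, which could disturb the sleep being measured.

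**Conclusion.** The tension in the text is genuine, but it is an ambiguity in one table cell and a possible feasibility limit, not a contradiction. Staff have to choose the active modalities when they set up the wrist sensor, and the battery limit they must respect is already written down.

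At worst, on an assumed 8 h night, one wrist channel loses 4-6 h (50-75%). That holds only if ACC+GYR is meant to run all night, the example battery life applies to the device worn, and power is not maintained. Actigraphy can still carry the comparison with the sleep log, and nothing in the protocol shows the ECG or skin temperature recordings to be affected. No sample size, error rate, named endpoint or conclusion changes. This is operational detail that the study team can be expected to fill sensibly, so no change to the plan is needed.

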### C. Clinical assessments

Clinical assessment will monitor patients during various clinical tests. Sensors will measure vital signs as well as movement and muscle activation in the upper and lower limbs. Sensor placement for these assessments is depicted in Figure 1:

**Figure 1:** Possible locations of sensor placement for patient clinical assessment

Sensor Type	Location	Modalities	Purpose	Clinical test
a	Left parasternal and mid-	ECG	Heart rate during/after	All

STU#: STU00205532

	clavicular line, Left parasternal line, Left mid- axillary line		test	
b	Pelvis, Wrists, Ankles, Foot (bilateral)	ACC+GYR+MAG	Movement detection, activity recognition	10MWT, 6MWT, TUG, gait analysis, FIM
c	Tibialis anterior, Hamstring, Rectus femoris (bilateral)	EMG+ACC or ACC+GYR+MAG	Muscle activation (spasticity detection)	MAS
			Joint angles of knee during walking, postural sway during standing	10MWT, 6MWT, TUG, gait analysis, BBS, FIM
	Biceps brachii (bilateral)	EMG+ACC	Muscle activation	MMT, ARAT, FIM
d	Hip (bilateral)	ACC (Hip)	Joint angles of hip during walking	10MWT, 6MWT, TUG, gait analysis, FIM

Participants will perform a series of common clinical tests that are used to evaluate functional performance after stroke. Clinical tests may include any of the following:

1. Modified Ashworth Scale (MAS)
2. 10-Meter Walk Test (10MWT)
3. 6-Minute Walk Test with or without VO2 analysis (6MWT)
4. Berg Balance Scale (BBS)
5. Functional Gait Assessment (FGA)
6. Quality Indicators (QI)
7. Timed Up and Go (TUG)
8. Manual Muscle Test (MMT)
9. Action Research Arm Test (ARAT)
10. Gait analysis using GaitRite: self-selected and slow and fast walking speeds (3 trials each)

All tests will be performed by a licensed physical therapist or occupational therapist. Therapist-reported outcomes for each test will be recorded separately. The participant will be given rest breaks as needed between tests to minimize fatigue. Therapist assistance and body-weight support will be provided as needed.

[figure not shown]
Research staff will be responsible for all sensor recording practices, such as instrumenting the sensors and marking therapy activities on a computer/tablet. Research staff will also keep a written log of activities as they are undertaken during the assessments, including notable events, amount and type of assistance, or use of

STU#: STU00205532

external devices. Logs will be consulted during analysis to compare with the timestamped sensor data.

#### **D. Swallowing/Speech assessment**

Swallowing/Speech assessment will monitor patients' swallow behavior during mealtimes, swallow behavior during bedside/videofluoroscopic swallow assessment, and speech behavior during speech and language therapy. All tests will be performed by a licensed speech-language pathologist, with assistance from research staff. One to three custom acoustomechanic sensors ([name] research group) will be placed as shown in Figure 2. The acoustomechanic sensors will be paired to a research smartphone to record all data from the devices.

**Figure 2:** Acoustomechanic sensor placement (bilateral to the hyolaryngeal complex, and/or at midline) for swallowing assessment

To measure swallowing during eating, sensors will be placed at least 15 minutes before scheduled mealtime. The participant will then be asked to eat their meal. During the meal, research staff will observe behavior and time stamp the swallowing events associated with eating. Additional observations will be made of coughs, wheezes, or gurgling noises. After the meal, research staff will observe the participant for at least 15 minutes afterward.

To measure swallowing during bedside or videofluoroscopic analysis, sensors will be placed immediately prior to the measurement. The videofluoroscopic swallow assessment will be performed only on those stroke patients for whom it is standard of care. Videofluoroscopic analysis is a radiologic examination of swallowing function that uses a special movie-type x-ray called fluoroscopy. The patient is observed swallowing various consistencies of barium-coated liquids and solid foods, in order to evaluate the ability to swallow safely and effectively. (Because this exam is part of the standard of care, a Radiation Dosimetry Form is not needed). Research staff will observe behavior and time stamp the swallowing events, coughs, wheezes, or gurgling noises for the acoustomechanic sensor throughout analysis.

[figure not shown]
To measure speech, sensors will be placed immediately prior to the patient's scheduled speech and language (SL) therapy. The sensor will monitor laryngeal activity during common SL exercises and during testing with the Western Aphasia

STU#: STU00205532

Battery-Revised (WAB-R). The Aphasia Quotient (AQ) of the WAB-R provides an overall quantitative metric of aphasia severity that is based on auditory comprehension and oral expression skills. Tasks of the AQ include naming pictures, repeating words and sentences, reading words and sentences aloud, describing pictures, and having a conversation.

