**1 OBJECTIVES:**

**Aim 1:** Assess the feasibility of continuous long-term monitoring of patients with stroke using wearable sensors.

We will obtain quantitative health data from research-grade, wireless, wearable sensors on individuals with subacute and chronic stroke in the clinical setting, as well as healthy controls.

We will specifically check for variability in device data, as well as consistency and periodicity of sensor readings across the clinical study period. We will analyze test-retest reliability and inter-rater reliability of using the wearable sensor technology for clinical and monitoring applications. Furthermore, we will determine whether the sensors can distinguish biometric and activity characteristics between healthy controls and individuals with stroke.

**Aim 2:** Quantify upper and lower extremity movement impairments, mobility-related activities, speech and swallowing activities, and clinical parameters during stroke recovery.

We will obtain continuous biometric and movement-based sensor data for clinical symptoms (e.g., muscle activation, heart rate variability, talk time, gait quality, and balance) during the performance of validated clinical tests and during general clinical activities (e.g., therapy, eating, and sleeping).

We will compare device data with clinically validated measures of movement and language function, such as the Modified Ashworth Scale or Western Aphasia Battery. We will describe variation of device data in subgroups of subjects defined by clinician assessed clinically validated measures (10-Meter Walk Test, Mini-Mental Status Exam, etc.). We will also assess the ability of the sensors to capture response to treatment, such as movement therapy, speech therapy, medication, and Botox by comparing sensor data before and after treatment. We will provide evidence about the degree to which the measured variables are intercorrelated. Lastly, we will evaluate and compare the state of recovery between patients at time of discharge using

STU#: STU00205532

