#### **D. Swallowing/Speech assessment**

Swallowing may be assessed in this laboratory visit, during a break from physical activities. Participants will be asked to complete oral facial movements and swallow a variety of food consistencies and a beverage. Participants may also be engaged in a brief (5-minute) conversation about an established topic to provide a representative sample of their typical language. Procedures for sensor use during this assessment are the same as that for inpatients, described in section 6.2.D.

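### Inpatient speech is recorded only around scheduled speech therapy, so an inpatient without a session has no described route to the consent or discharge speech recording

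*Protocol*

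**What the plan says.** Aim 2 (Protocol section 1) is to "Quantify upper and lower extremity movement impairments, mobility-related activities, speech and swallowing activities, and clinical parameters during stroke recovery", and it ends with a comparison of patients' sensor-based state of recovery at discharge. For inpatients, section 5 states "Assessments will be completed a minimum of two times", on consent and at discharge. Its table gives 2 to 10 swallowing/speech assessments for stroke participants.

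Section 6.2.D sets out how this is done for inpatients:

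- **Speech.** The only setting named is "speech behavior during speech and language therapy". The trigger is "To measure speech, sensors will be placed immediately prior to the patient's scheduled speech and language (SL) therapy". WAB-R testing is described in the same paragraph.
- **Swallowing at meals.** "To measure swallowing during eating, sensors will be placed at least 15 minutes before scheduled mealtime". Research staff time-stamp the swallows, and no clinical indication is required.
- **Swallowing at examination.** "To measure swallowing during bedside or videofluoroscopic analysis, sensors will be placed immediately prior to the measurement". For the X-ray examination, "The videofluoroscopic swallow assessment will be performed only on those stroke patients for whom it is standard of care".

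For chronic stroke participants and healthy controls, section 6.3.D has a task that needs no therapy order: "Participants may also be engaged in a brief (5-minute) conversation about an established topic to provide a representative sample of their typical language".

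**The concern.** A scheduled speech and language session is not a neutral calendar slot. Patients have one because their speech or language is judged to need it. The condition for recording is therefore linked to the quantity being recorded. A patient who recovers early may have no session left near discharge, and a patient with little speech deficit may never have one.

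Two things are at stake. First, speech change from admission to discharge, and speech status at discharge, would describe inpatients who were under speech therapy at those times rather than stroke inpatients generally. No later analysis can recover recordings that were never made, so the matter belongs in the protocol.

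Second, Aim 1 and section 7 plan comparisons with healthy controls. Inpatient speech would come from therapy exercises and WAB-R testing, and control speech from an optional conversation. A difference between the groups would then mix the effect of stroke with the effect of the task.

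**Working it through.** The protocol states no figure on this point, so there is none to reproduce. The check is a reading of the routes to a discharge recording, followed by an illustration of direction on assumed inputs.

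**Step 1: routes to a discharge recording under section 6.2.D**

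| Measurement | Route described | Depends on need for care? |
|---|---|---|
| Speech, including WAB-R | Scheduled speech and language therapy | Yes; no other route named |
| Swallowing | Mealtime recording | No |
| Swallowing | Bedside assessment | Not limited to patients for whom videofluoroscopy is standard of care |
| Swallowing reference | Videofluoroscopy | Yes, by design |

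Only speech lacks a route that is independent of care need.

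**Step 2: direction among patients measured at admission**

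Assumptions, none from the protocol: admission score B with SD 1; change C with mean 0.50 and SD 0.5; discharge score Y = B + C; joint normality. A fraction f of patients lacks the discharge value. Write z for the (1 − f) normal quantile and k = φ(z)/(1 − f). Then k = 0.195, 0.350 and 0.497 for f = 10%, 20% and 30%.

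*Loss of those with the largest change.* Observed mean = 0.50 − 0.5k:

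- f = 10%: 0.50 − 0.5 × 0.195 = 0.40
- f = 20%: 0.50 − 0.5 × 0.350 = 0.33 (0.325 before rounding)
- f = 30%: 0.50 − 0.5 × 0.497 = 0.25

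*Loss of those with the highest discharge score.* Observed mean = 0.50 − [cov(C,Y)/SD(Y)] × k. If s is the slope of change on baseline, cov(C,Y) = 0.25 + s and SD(Y) = √(1.25 + 2s). At f = 30%:

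- s = 0: 0.50 − (0.25/1.118) × 0.497 = 0.39
- s = −0.2 (correlation −0.4): 0.50 − (0.05/0.922) × 0.497 = 0.47
- s = +0.2 (correlation +0.4): 0.50 − (0.45/1.285) × 0.497 = 0.33
- s = −0.3: 0.50 + (0.05/0.806) × 0.497 = 0.53

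A simulation of 400,000 patients for correlations −0.4, 0 and +0.4 agrees with these results to within 0.003. Under random loss the mean stays at 0.50.

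Loss ranked on change always understates the mean. Loss ranked on discharge level understates it unless s falls below −0.25, where cov(C,Y) changes sign.

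**Step 3: if therapy usually runs to discharge**

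Take the top 30% by change, but let 90% of them still have a session. The lower 70% have mean change 0.252. The top 30% have mean 0.50 + 0.5 × 0.348/0.30 = 1.080. Observed mean = (0.70 × 0.252 + 0.27 × 1.080)/0.97 = 0.48, about 4% below 0.50.

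**Step 4: patients never scheduled**

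These have neither recording. If they start with little deficit and change little, leaving them out raises the observed mean relative to all inpatients, which is opposite to the main case in Step 2.

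**The case against.** The strongest case against the point has five parts.

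*Therapy may run to discharge.* Section 5 plans a discharge assessment, and the protocol gives no rate of early ending. This stands as a limit on size: Step 3 shows how small the effect could be. It does not supply a route for a patient without a session.

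*Not every inpatient is promised a speech assessment.* Section 5 allows up to four assessment types per inpatient, and no mean speech change is named as an endpoint. This is true, but it leaves the therapy schedule to decide who is recorded, and Aim 2 still compares patients at discharge.

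*Aim 2 mentions talk time during general activities, including eating.* The laryngeal sensor is worn at meals and might capture speech there. However, section 6.2.D describes that recording for swallowing and asks staff to time-stamp swallows. It gives no speech task or speech label at meals.

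*The direction is not established.* This stands. Steps 2 and 4 show cases on both sides of zero, and dropout or medical withdrawal could also act the other way.

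*The tasks overlap in part.* The WAB-R Aphasia Quotient already includes a conversation. This softens the contrast with controls, but only for inpatients who have the WAB-R.

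A reader might also infer that patients whose swallowing recovers lose their discharge measurement. The text does not support that, because mealtime and bedside recording remain. Nor does it support a figure for weakened agreement with videofluoroscopy through restricted range. The protocol specifies no between-patient correlation with a videofluoroscopic score. It describes time-stamped events and event classification, and Table 1 reports sensor data already collected on 5 healthy controls and 10 persons with aphasia. Limiting an X-ray examination to standard of care is a reasoned choice.

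**Conclusion.** The point holds for speech. As written, an inpatient without a scheduled speech and language session has no described way to give the consent or discharge speech recording, so the availability of the outcome depends on speech function. Admission-to-discharge speech change and speech status at discharge would be estimated in a selected group, and the comparison with controls would rest on different tasks.

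Neither size nor sign can be fixed from the protocol. Among patients measured at admission, loss of the best-recovered would understate change. With an assumed true mean of 0.50 SD, the observed mean falls to 0.40, 0.33 or 0.25 when the 10%, 20% or 30% with the largest change are lost. It is close to unbiased if nearly all still have a session. It can be biased upward if more impaired patients improve much more, or if the target is all inpatients. A firm statement that speech recovery is understated would go beyond the text.

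For swallowing, the only limit is that the inpatient videofluoroscopic reference covers referred patients, which is a matter of stated scope.

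**What to change.** In section 6.2.D:

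1. Record the 5-minute conversation of section 6.3.D for every inpatient able to take part in the swallowing/speech assessment, at both the consent and discharge sessions, whether or not speech therapy is scheduled. Name it as the common speech measure for recovery and for comparison with controls. Because section 6.3.D makes the conversation optional, make it a standard part of that assessment there too.
2. Keep the therapy-session and WAB-R recordings as a validation subset.
3. State that inpatient agreement with videofluoroscopy applies to patients referred for that examination.

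The cost is protocol wording and about 5 extra minutes at each of two sessions, with the same sensors and a task already in the protocol. The conversation yields no Aphasia Quotient, so that comparator stays missing for inpatients without WAB-R testing. No change is proposed to who receives therapy or videofluoroscopy.
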